8.5.2. Use of Cornstarch (or Glycosade)

The prescribed and actual daily amount and frequency of cornstarch over time will be summarized by study visit in a table and provided in the listings. In addition, the percent change from baseline in daily cornstarch amount by study visit by subject by dosing cohort will be plotted. Daily frequency of cornstarch (total and by daytime, nighttime, and bedtime) by study visit will be plotted for each subject.

Data collected at a scheduled visit within an analysis window of +/- 14 days of the target day for a visit will be included in the analysis. If such a scheduled visit is not performed, data collected at the nearest unscheduled visit (if any) completed within that analysis window will be included.

8.5.3. Continuous Glucose Monitoring

Continuous glucose monitoring (CGM) device data will be collected from cohort 3 and 4 subjects for this study. Glucose data will be summarized per subject per week and per subject per week per day (24 hours) Raw summary statistics will be provided. Study weeks are derived by (assessment dates – dosing date +1)/7.

Percentage of time spent in normal glucose ranges (between 60 mg/dL -120 mg/dL, between 70 mg/dL - 120 mg/dL), percentage of time spent in low and high glucose values (< 60 mg/dL, < 70 mg/dL, < 50 mg/dL, > 120 mg/dL), number of low glycemic events (< 60 mg/dL,

<70 mg/dL, <50 mg/dL), time spent in minutes under glucose values (< 60 mg/dL, < 70 mg/dL, < 50 mg/dL), time spent in minutes for glucose ranging in (60 - 120, 70 - 120 and > 120 mg/dL) will be summarized by subject by week and by subject by week by day (24 hours).

Percentage of time spent in any glucose range in a week is calculated as time duration (minutes) of glucose values spent in that range in a week, divided by total time duration (minutes) in a week and multiplied by 100 where

- Time duration (in minutes) of glucose values spent in that range in a week= sum of all the time intervals where glucose value is in the range where time interval for any glucose value is calculated as the difference between collection time of that glucose value and the next collection time. If the glucose value is missing at any collection time between first glucose value and last glucose value collected in that week, the last available glucose value prior to the collection time will be carried over.
- Total time duration (in minutes) in a week= (Last time/date of non-missing glucose value of the week first time/date of non-missing glucose value) + 5 minutes
- Only glucose value between 40 and 400 mg/dL collected by CGM device will be considered as non-missing value.

The percentage of time spent in a glucose range in an hour will be calculated in similar fashion where only recordings in that hour will be considered. Percentage time spent in a glucose range in a month (4-weeks) will be calculated by calculating the percentage time spent in each week and taking average of these weekly values.

The percentage of subjects with >=85% of weekly glucose values in the range 60-120 mg/dL and >=90% of glucose values in the range 60-120 mg/dL will be summarized by week for each cohort. Summary of total time spent, percent of time spent, and average time of episodes in glucose ranges (<60, <70, 60-120, 70-120, > 120 mg/dL) will be provided by week and by day (24 hours) for all subjects combined.

In addition, individual glucose profile over 24 hours together with cornstarch prescription will be plotted weekly (up to 7 days) by subject. Summary of glucose values (mean, median, min, max, etc.) will be plotted by study days for each subject. Summary of glucose values (mean, min, max) will be plotted by day (24 hours) and week for each subject. Variability (SD) of glucose values in a week will be plotted by week for each subject.

Number of low glycemic events and their duration will be summarized by week for each subject. Number of low glycemic events will be plotted by study days and by week for each subject. A low glycemic (hypoglycemic) event is defined as a series of at least two sensor glucose values less than 60 mg/dL, lasting at least 15 min, with no intervening values of 60 mg/dL or more. The end of a hypoglycemic event is defined as a minimum of 15 consecutive minutes with at least two sensor glucose values of at least 60 mg/dL and at least 10 mg/dL above the nadir of the event or at the end of a week. Further, daily, and weekly number of low glycemic events together with cornstarch use will be plotted for each subject. For cornstarch use, data collected at all visits (scheduled and unscheduled) will be included in the analysis.

Percentage of time of glucose values under 60 mg/dL, percentage of time spent in normal glucose ranges (between 60 mg - 120 mg/dL), total time (minutes) of glucose values under 60 mg/dL will be plotted by subject by week.

Percentage of time spent in normal glucose ranges (60–120 mg/dL) together with cornstarch intake will be plotted by week for each subject, by week for each cohort, and by month (4-weeks) for each cohort. Percentage of time spent in different glucose ranges (<60, 60 – 120, >120 mg/dL) together with cornstarch intake (in grams) will be plotted by month (4-weeks) for each cohort. Total time (minutes) of glucose values under 60 mg/dL together with cornstarch intake will be plotted by week for each subject.

Additional cutoffs and glucose variability may be analyzed as appropriate. Additional summary may be performed by dosing cohort by week.

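### The weekly CGM time-in-range rule carries one reading across sensor gaps of any length and keeps the gap in the denominator, so a long gap can misstate a subject-week

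*SAP*

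**What the plan says.** SAP 8.5.3 builds the weekly percentage in a glucose range from time intervals. In the numerator, the "time interval for any glucose value is calculated as the difference between collection time of that glucose value and the next collection time". Missing readings are handled as follows: "If the glucose value is missing at any collection time between first glucose value and last glucose value collected in that week", then "the last available glucose value prior to the collection time will be carried over". The denominator is the time of the last non-missing reading of the week minus the "first time/date of non-missing glucose value) + 5 minutes".

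The hourly percentage follows the same method, "where only recordings in that hour will be considered". The 4-week percentage is found by computing each weekly figure and "taking average of these weekly values".

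No maximum carry-forward time, and no rule for weeks with long gaps, appears anywhere in SAP 8.5.3. The general missing-data text in SAP 7.2 adds none. Protocol 8.1.2 covers wearing the device and transferring the data, and Protocol 10.2.3.2 leaves the analysis to the SAP.

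**The concern.** Carrying a value over a few missed readings is harmless. Carrying it over half a day or a day treats glucose as constant for all that time, and because the gap stays in the denominator, the assumed value carries the full weight of the missing time. A subject's weekly figure can then turn on one reading.

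The rule also treats equal gaps unequally. A gap at the start or end of a week falls outside the span from first to last reading and leaves the denominator. The same gap in mid-week stays in and is filled.

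Gaps are foreseeable. Protocol 8.1.2 asks subjects to wear the device through Week 52. Protocol 3.2.2.1 and 3.2.3.3 schedule a procedure after the fasting challenge so that the sensor need not be replaced beforehand. Protocol 8.1.3 provides for subjects who cannot use the device.

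At stake are the weekly and 4-week time-in-range summaries and the total minutes below 60 mg/dL, several of them plotted with cornstarch intake. Only Cohorts 3 and 4 have CGM data, with 3 subjects planned in each, so one misstated week has little to dilute it.

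**Working it through.** The plan states no figure to reproduce, so the check applies its rule to assumed weeks.

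**Inputs from SAP 8.5.3 and 8.1.1:** uncapped carry-forward; denominator equal to last minus first reading time plus 5 minutes; 3 subjects per cohort; 4-week figure equal to the plain mean of weekly figures.

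**Assumptions, not in the documents:** readings every 5 minutes (suggested by the 5-minute term); readings at both ends of the week; observed time in range p = 85%; one interior gap of 30 minutes to 24 h.

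**Check without a gap.** A week has 2,016 readings at 5-minute spacing. The denominator is 2,015 x 5 + 5 = 10,080 minutes, the whole week, so the rule returns the observed share.

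**With a gap.** Let f = gap / 10,080 minutes.

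- Carried value in range: p(1 - f) + f, an error of +(1 - p)f.
- Carried value out of range: p(1 - f), an error of -pf.

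The result is the same whether blank rows are kept and filled, or are absent so that the reading before the gap runs to the next collection time.

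| Gap | f | Carried value in range | Carried value out of range |
|---|---|---|---|
| 30 min | 0.0030 | 85.04% (+0.04) | 84.75% (-0.25) |
| 6 h | 0.0357 | 85.54% (+0.54) | 81.96% (-3.04) |
| 12 h | 0.0714 | 86.07% (+1.07) | 78.93% (-6.07) |
| 24 h | 0.1429 | 87.14% (+2.14) | 72.86% (-12.14) |

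For 24 h, f = 1,440 / 10,080 = 1/7, so the two results are 0.85 x 6/7 + 1/7 = 6.1/7 and 0.85 x 6/7 = 5.1/7.

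**Other observed shares, 24 h gap:** 80% becomes 82.9% or 68.6%; 90% becomes 91.4% or 77.1%; 95% becomes 95.7% or 81.4%.

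**Minutes below 60 mg/dL.** If the reading before a 24 h gap is below 60, the rule adds about 24 x 60 = 1,440 minutes.

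**Cohort summaries.** The larger 24 h error moves a 3-subject weekly mean by 12.14/3 = 4.0 points and a 3-subject 4-week mean by 12.14/12 = 1.0 point. With an in-range carry the shifts are 2.14/3 = 0.7 and 2.14/12 = 0.2.

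**Average bias.** If a gap starts without regard to glucose level, the carried value is in range with probability p. The expected error is p(1 - p)f - (1 - p)pf = 0. Individual weeks are misstated, but the average is not shifted.

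**After the fix.** With the gap out of numerator and denominator, the result is 85% whatever the gap length or the last value.

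**Last reading.** The denominator gives the last reading of a period 5 minutes. The numerator refers it to a next collection time, which may lie in the next week and does not exist when an hour is processed alone. For a full week, 5 minutes is 5/10,080 = 0.05%.

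**The case against.** The strongest reply is that little depends on this. Protocol 8.1.2 calls the CGM data supplemental, and the SAP change history describes the added CGM work as exploratory. No test, decision rule, or primary or secondary endpoint uses it. The rule is explicit and computable. The large errors need both a gap of many hours and an out-of-range last value: with 85% observed time in range and a randomly placed gap, that is the 15% case of an assumed event. Raw summaries, individual 24-hour profiles and low-glucose event counts requiring at least two sensor values are also planned, and SAP 7.2 keeps listings to observed data unless stated otherwise. A careful reader could spot a long gap. All of this stands and limits the weight of the point. It does not make crediting a day of missing time to one reading a sound summary.

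A reader might infer three stronger things that the documents do not support.

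- That gaps change which subjects meet the responder cut-offs. SAP 8.5.3 words that summary as "The percentage of subjects with >=85% of weekly glucose values in the range 60-120 mg/dL", which counts values rather than time. It does not say that carried values enter the count. Asking for a time-based count could bring the carry-forward rule into a summary that may not use it.
- That range percentages will fail to sum to 100%. Sums such as 116.7% for a week (10,080/8,640, when a 24 h week-end gap is credited from the following week) or 91.7% for an hour (55/60, when the last reading gets no time) need particular programming choices. The 5-minute term in the denominator argues against both.
- That extreme readings are mishandled by oversight. The SAP is explicit: "Only glucose value between 40 and 400 mg/dL collected by CGM device will be considered as non-missing value". Recoding them would reverse a stated rule, and the documents do not describe the device output that would justify doing so.

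**Conclusion.** The point holds. As written, SAP 8.5.3 assigns any interior sensor gap, however long, to the range of one reading and counts it as observed time. In a full week with 85% observed time in range, an assumed 12 h gap gives errors of +1.1 or -6.1 points and a 24 h gap +2.1 or -12.1 points. Gaps of 30 minutes are negligible, so a limit on gap length is the right kind of repair.

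The size rests on assumed gap lengths, observed shares and 5-minute sampling; the documents do not say how often long gaps occur. The effect is confined to supplemental, descriptive CGM summaries in Cohorts 3 and 4. The primary and secondary endpoints are untouched, and randomly placed gaps give noise, not average bias. It is a worthwhile improvement to a clear rule, and does not call the trial's main conclusions into question. The last-reading mismatch is a minor alignment.

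**What to change.** In SAP 8.5.3:

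1. Carry the last value forward only over gaps up to a short maximum, chosen by the sponsor and stated before the analysis. Remove longer gaps from both numerator and denominator.
2. Show observed minutes beside each weekly percentage and each weekly total of minutes below 60 mg/dL. Without them, totals cannot be compared between weeks with different wear. They also expose thin weeks without excluding any subject.
3. As a minor alignment, count the last reading of each week or hour as 5 minutes in the numerator, to match the denominator.

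No new data are needed. The cost is reprogramming the CGM derivation and the tables and plots built on it. Some weeks will rest on less observed time yet still count equally in the 4-week average. Removing long gaps also assumes that unobserved time resembles observed time, which is a weaker assumption than constant glucose but still an assumption.

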### **3.2.2.2. Baseline Visit – Day 1**

The assessments and procedures to be performed on Day 1 are listed in the Schedule of Events (Table 6).

Following completion of the Day 0 assessments (ie, controlled fasting challenge and 24-hour urine collection), subjects will receive a single, peripheral IV infusion of DTX401. Safety (vital sign measurements [Section 8.2.1], clinical laboratory assessments [Section 8.2.6], and AEs and SAEs [Section 9.1]) will be monitored over 24 hours following infusion of DTX401 (Table 6). Any AEs that occur during this 24-hour observation period will be treated with appropriate supportive and medical care deemed necessary for the well-being of the subject.

Subjects will be discharged after a 24-hour observation period. Subjects in Cohort 3 will be discharged with prednisone to allow rapid treatment of possible vector-induced hepatitis if it occurs following treatment with DTX401 (Section 8.2.6.2.1). Subjects in Cohort 4 will be discharged with prednisone per the prophylactic steroid regimen (Section 8.2.6.2.2).

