#### **8.1.1. Symptom-Free Euglycemia (Controlled Fasting Challenge)**

The subject's ability to maintain symptom-free euglycemia during a controlled fasting challenge will be assessed at time points specified in the Schedule of Events. However, if clinically indicated, the controlled fasting challenge can also be performed at an unscheduled visit.

The controlled fasting challenge requires a 24-hour inpatient stay in a hospital or research facility and will be performed after all other study visit assessments (except [REDACTED]) have been completed and the required laboratory assessments (as specified below) have been reviewed by the Investigator (or a subinvestigator assigned to review results and make clinical decisions per the site delegation log). Subjects should wear their CGM device throughout the fasting challenge, and should not change the sensor prior to the assessment.

If a subject is suspected to have HPA axis impairment (eg, due to prolonged steroid treatment; may be confirmed by morning cortisol or stimulation tests), the fasting challenge may have to be rescheduled to a later date in order to ensure subject safety and provide interpretable results.

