Before the controlled fasting challenge begins, the study site will provide dinner for the subject. The dinner meal will be personalized for each subject, and will include a target carbohydrate range and overall composition in protein, fats and dietary fibers that is as close as possible to the subject's most current dinner prescription, but not higher in carbohydrate content than the dinner consumed at their baseline fasting challenge. The start and stop time of the dinner meal and its full dietary composition including amount of carbohydrates consumed will be recorded. After dinner, subjects will be given an oral dose of cornstarch equivalent per their most recent cornstarch prescription, at approximately the same time that they typically take it, but no later than 3 hours post dinner. The amount of cornstarch administered should not be higher than that consumed by the subject at the baseline fasting challenge. The time of ingestion of prefasting cornstarch and the amount consumed will be recorded. After the cornstarch is ingested, the controlled fasting challenge will begin, and the start time will be recorded accordingly. If a subject does not receive cornstarch before going to bed at the time of the CFC, the fasting challenge will start after they complete their dinner. Subjects will be instructed to minimize activity after they finish eating dinner until the end of the controlled fasting challenge.

During the fast, subjects may not ingest any food or drink other than water. The controlled fasting challenge will end when the subject's glucose level decreases to  $< 54$  mg/dL ( $< 3.0$  mmol/L) or when the subjects experience signs and symptoms of hypoglycemia, or when the fast reaches 15 hours without hypoglycemia, whichever occurs first. The stop time of the controlled fasting challenge will be recorded. At the end of the controlled fasting challenge, the subject's hypoglycemia should be treated per the institution's standard procedure, which may include providing the subject with a meal, cornstarch, or IV glucose, if medically indicated.

In cases where the controlled fasting challenge is terminated prematurely before the subject reaches a glucose level of < 54mg/dL or without the subject experiencing signs and symptoms of hypoglycemia, or due to any deviation in the fasting challenge protocol, an ad hoc fasting challenge may be scheduled within 6 weeks from the scheduled fasting challenge.

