### **8.1.2. Continuous Glucose Monitoring**

Supplemental information on glucose level trends will be collected using a continuous glucose monitoring (CGM) device. The site will provide a CGM device to the subject during the Screening Period after determining that the subject is eligible for the study (Table 6). Subjects will be educated on the appropriate care and use of the CGM device and sensors, and instructed to wear the CGM device through the Week 52 visit or early withdrawal. Data from the subject's CGM device will be transferred to the Sponsor throughout the study, including a final data transfer at the end of the Week 52 visit or early withdrawal. Details regarding the care and use of the CGM device and sensors and data transfer to the Sponsor are provided in the Manual of Operations.

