### **10.2.3. Efficacy Analyses**

#### **10.2.3.1. Symptom-Free Euglycemia**

The time (in minutes) to the first hypoglycemic event (defined as glucose  $< 54$  mg/dL [ $< 3.0$  mmol/L]) during a controlled fasting challenge will be determined for all subjects at Day 0 and Weeks 12, 24, and 52. Full details of the analysis will be provided in the SAP.

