8.5. Efficacy Analysis

8.5.1. Symptom-Free Euglycemia

The time (in minutes) to the first hypoglycemic event (defined as glucose <60 mg/dL [<3.3 mmol/L]) during a controlled fasting challenge at baseline (Day 0), Week 12, 24 and 52, and the change from baseline in time (in minutes) to first hypoglycemic event at Weeks 12, 24, and 52 will be summarized. If the controlled fasting challenge has to be stopped due to symptomatic hypoglycemic event, or the subject is administered intervention (e.g., cornstarch), the time to the first hypoglycemic event will be defined as the time to the controlled fasting challenge is terminated. If there is no hypoglycemic event during the fasting challenge, the time will be censored at the maximum evaluable time (15 hours).

A listing of the controlled fasting challenges and the glucose, lactate, and other local lab parameters (cortisol, free fatty acids, glucagon etc.), and capillary glucose levels (if available) collected during the controlled fasting challenges will be provided. Use of cornstarch and carbohydrates in the dinner prior to controlled fasting challenge and change from baseline will be summarized by visit.

In addition, plots for individual patient profile of controlled fasting challenge hours, plots for individual patient profile of glucose and lactate during controlled fasting challenges will be presented by study visits.

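### SAP 8.5.3 does not separate fasting-challenge time from ordinary CGM wear, so a low provoked by the test can be counted like a low at home (Cohorts 3 and 4)

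*SAP*

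**What the plan says.** **CGM wear.** Protocol 8.1.2: "The site will provide a CGM device to the subject during the Screening Period after determining that the subject is eligible for the study". Subjects are then "instructed to wear the CGM device through the Week 52 visit or early withdrawal". Protocol 8.1.1 adds: "Subjects should wear their CGM device throughout the fasting challenge, and should not change the sensor prior to the assessment". Sections 3.2.2.1 and 3.2.3.3 repeat this for Day 0 and for the inpatient follow-up visits.

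**The challenge.** Only water is allowed. The test ends when glucose is below 54 mg/dL, when there are signs and symptoms of hypoglycemia, or "when the fast reaches 15 hours without hypoglycemia, whichever occurs first" (Protocol 8.1.1). Start and stop times are recorded. Time to hypoglycemia "will be determined for all subjects at Day 0 and Weeks 12, 24, and 52" (Protocol 10.2.3.1), and unscheduled and ad hoc challenges are also allowed. The baseline challenge precedes dosing: "Following completion of the Day 0 assessments (ie, controlled fasting challenge and 24-hour urine collection), subjects will receive a single, peripheral IV infusion" (Protocol 3.2.2.2).

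**The CGM analysis.** SAP 8.5.3 covers Cohorts 3 and 4. It defines a low glycemic event as at least two sensor values below 60 mg/dL, lasting at least 15 min, with no intervening value of 60 or more. It then says: "Number of low glycemic events and their duration will be summarized by week for each subject". Time in ranges, minimum, mean and SD are also reported by day or week. The only data filter is on value: readings outside 40 to 400 mg/dL count as missing. Missing readings within a week are filled with the last available value, and weekly duration runs from the first to the last reading plus 5 min. Nothing excludes, flags or separately reports challenge or inpatient time, and SAP section 9 lists no changes.

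**The concern.** The challenge deliberately fasts the subject towards a low, while home CGM shows what happens under the subject's own diet and cornstarch. The event definition does not distinguish the two settings.

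This matters because the protocol itself relies on the contrast. Sections 1.3.1 and 3.1 set the absence of nocturnal hypoglycemia on CGM against shorter fasting times in the inpatient test. The challenge starts after dinner and can run overnight, so pooling mixes the two settings in the same hours of the day.

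The mixing also depends on response. A subject who completes 15 h without a low contributes no induced event, and one whose glucose falls can contribute one. To that extent CGM is not independent evidence on glucose at home. The analysis has two cohorts of nominally 3 subjects, and many outputs are per-subject daily or weekly plots, where a single induced event is visible.

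**Working it through.** The plan gives no figure to reproduce here. The check has three parts.

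**1. Can a challenge low meet the event definition?** Once glucose is at or below 70 mg/dL, STAT samples are about 30 min apart and results should be available within 30 min (Protocol 8.1.1). From crossing 54 mg/dL to a STAT result can therefore take up to about 30 + 30 = 60 min. Capillary glucose at the same time points may shorten this. A run of 15 min below 60 mg/dL is thus plausible in a challenge that ends on low glucose. The documents do not give the duration, so it is assumed below.

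**2. Size per affected week.** A full week is 7 × 24 × 60 = 10,080 min, and a day is 1,440 min. The added percentage of time below 60 mg/dL is 100 × minutes / record length. The 4-week figure is the weekly figure divided by 4, because SAP 8.5.3 averages weekly values.

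| Assumed low (min) | Of a 24 h day | Of a full week | 4-week average |
|---|---|---|---|
| 15 | 1.04% | 0.15% | 0.04% |
| 30 | 2.08% | 0.30% | 0.07% |
| 60 | 4.17% | 0.60% | 0.15% |
| 90 | 6.25% | 0.89% | 0.22% |
| 120 | 8.33% | 1.19% | 0.30% |

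The event count rises by about 1 if the definition is met. The responder cut-offs of 85% and 90% in 60–120 mg/dL allow 0.15 × 10,080 = 1,512 min and 0.10 × 10,080 = 1,008 min out of range in a full week. A low of 15 to 120 min alone would rarely change that status.

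**3. Which week receives the baseline low?** The SAP formula is (assessment date − dosing date + 1)/7, with no rounding rule. Protocol Day 0 gives (−1 + 1)/7 = 0. The dosing date (Day 1) gives (0 + 1)/7 = 0.143.

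| Rounding | Low before midnight, Day 0 | Low after midnight, Day 1 | Days in Week 0 |
|---|---|---|---|
| Up | Week 0 | Week 1 | −6 to 0 |
| Down | Week 0 | Week 0 | 0 to 6 |
| Nearest | Week 0 | Week 0 | −3 to 3 |

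Assume the challenge starts between 18:00 and 22:00. A low at 7 h, the median that Protocol 1.3.1 cites for cornstarch, falls between 01:00 and 05:00 on the dosing date. With rounding up, it is counted in Week 1, a post-dose week. With rounding down or to nearest, Week 0 mixes pre-dose and post-dose days.

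For follow-up visits, taking the windows in the Schedule of Events (±2 days at Day 84, ±7 days at Weeks 24 and 52) and rounding up, challenges fall in Weeks 12–13, 23–25 and 51–53.

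**The case against.** The strongest reply is that CGM is supplemental and descriptive, the numerical effect is small, and a low on a challenge night can be recognised by setting the per-subject plots beside the challenge listing in SAP 8.5.1. The first two parts stand and limit the importance of the point. The third helps only a reader who cross-checks by hand. It does not correct event counts, minima, SDs or cohort summaries.

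A second reply is that exposure may be less than complete. Wear is phrased as something subjects *should* do. Protocol 1.3.1 shows that Cohort 3 already had Week 52 challenge data when Amendment 6 was written, so those challenges stopped at 60 mg/dL rather than 54, leaving less time below 60. The documents do not show that Cohort 3 sensors recorded them. Symptom-terminated challenges may not reach 60 at all, and the Week 12 visit may become an outpatient visit. This stands too, and it is why the artefact is described as possible per challenge and not certain.

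A reader might go further and infer that the pre-dose CGM week always holds an induced low while nearly all post-dose weeks do not, so that events would fall after dosing with no treatment effect. The documents do not support this. The challenge does precede the infusion, but the date-based formula can put the low itself in Week 1 or in a mixed week. Induced lows at Weeks 12, 24 or 52 push the other way. SAP 8.5.3 also plans no CGM change from baseline, whereas 8.5.1 and 8.5.2 do plan changes from baseline for their measures.

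**Conclusion.** The concern holds as a matter of analysis definition, for Cohorts 3 and 4. As written, SAP 8.5.3 treats a low provoked by the challenge like any other low, around Day 0/Day 1 and Weeks 12, 24 and 52, and at any ad hoc challenge. The size is about one extra event per challenge that ends on a qualifying low, and none for a subject who fasts 15 h without one. The minimum falls and the SD rises in that day and week. Time below 60 mg/dL rises by about 0.15 to 1.2 percentage points of a full week.

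These figures rest on an assumed 15 to 120 min low, a complete week of readings, and the sensor being worn as instructed. A shorter record would raise the percentage, but the documents do not state how much pre-dose CGM there is. The direction of any pre/post distortion cannot be stated. The primary and secondary endpoints are not affected. It is a correction worth making because it is cheap and removes an artefact that depends on response.

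**What to change.** In SAP 8.5.3:

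- Exclude from the main CGM summaries, event counts and plots the interval from the recorded challenge start to a prespecified time after the recorded stop. Apply this to every scheduled and unscheduled challenge.
- Remove the interval from both numerator and denominator, and do not carry values forward across it. Otherwise the existing carry-forward and first-to-last duration rules would refill the gap.
- Report challenge-period CGM separately, with the SAP 8.5.1 profiles, and show results including it as a sensitivity display.
- Define pre-dose and post-dose CGM weeks by date and time relative to the infusion, with an explicit rounding rule.

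The cost is SAP wording and a date/time filter on times already recorded. With a 2 h tail, chosen here only for illustration, up to 15 + 2 = 17 h of CGM is lost per challenge week: 1,020/10,080 = 10.1% of a full week. Those data remain visible in the separate and sensitivity displays.
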